5 STATISTICS AND METHODOLOGY

5.1 Translation plan

The translation of the SIRSI and TSK-SI into a German follows the guideline of Beaton et al (2000) however little adjustments were made. The original SIRSI was translated into five German versions. Two by two researchers, one with background in occupational therapy and psychology ([name]) and one with a background in physiotherapy ([name]). One by a patient with a history of shoulder dislocations, conservative therapy, surgery and return to sports. One online translation by deepl.com (https://www.deepl.com/translator, accessed on 20.02.2024) and the available German version by the German insurance company ((Returnto-Competition Schulter: Shoulder Instability-Return to Sport after Injury (SIRSI)-Skala (vbg.de), accessed 23.01.2024). The TSK-SI was translated into four German versions. Two by two researchers, one with background in sport science and data management ([name]) and one with a background in physiotherapy ([name]). One by the same patient described above and one again by deepl.com (https://www.deepl.com/translator, accessed on 29.05.2024) From these versions a consensus version for the SIRSI was developed by [name] and [name] and the TSK-SI by [name] and [name]. Then a backtranslation was done by an English native speaker. The resulting English version was compared to the original SIRSI and TSK-SI and the German version was adapted by the respective researchers. Another backtranslation was then done to check for successful adaptations. No further adjustments were made. The German version of the SIRSI was then named SIRSI-D and TSK-SI was named TSK-SI-D. The SIRSI-D and TSK-SI-Dwas pilot tested on 20 patients each, who attend to outpatient physiotherapy at the Schulthess Klinik. The SIRSI-D will be handed out on paper alongside with a brief feedback sheet. The sheets are returned to the PI and if decided useful by the researchers, the suggestions of the patients are incorporated into the final SIRSI-D or TSK-SI-D version that are used for the further validation process.

5.2 Statistical analysis plan

The reliability and validity of the German version of the Shoulder Instability-Return to Sport after Injury (SIRSI-D) and Tampa Scale of Kinesiophobia-Shoulder Instability (TSK-SI-D) score will be assessed through rigorous psychometric evaluation procedures.

Reliability will be evaluated to ensure the consistency and stability of the questionnaire over time.

Internal consistency, which measures the extent to which items within the questionnaire are correlated with one another, will be assessed using Cronbach's alpha coefficient. Test-retest reliability will be examined by administering the questionnaire to participants on two different timepoints one week apart and calculating the correlation between their scores.

Validity will be assessed to determine the extent to which the questionnaire measures the intended constructs of shoulder instability and return to sport after injury.

Content validity will be established by ensuring that the items in the questionnaire adequately cover all relevant aspects of the constructs.

Construct validity will be evaluated through factor analysis to confirm the underlying factor structure of the questionnaire and assess its convergent and divergent validity with other related measures.

Criterion validity will be examined through concurrent validity by comparing the scores of the SIRSI-D and TSK-SI-D questionnaire with SSV and WOSI.

Overall, these psychometric evaluation procedures will ensure that the German version of the SIRSI and TSK-SI-D scores are both reliable and valid for assessing shoulder instability and return to sport after injury in a German-speaking population. All statistical analyses are conducted in R (R Core Team (2022)).

5.3 Handling of missing data

Missing Data is reduced by the "soft required function" in REDCap, where patients are reminded if a question is not filled in but proceeding is possible. The exception are the checks of the inclusion criteria which are mandatory to proceed. This ensures that patients do not drop out completely. In addition, patients will be contacted via mail via a researcher, if an item is missing. In the analysis missing items in the WOSI, TSK-SI-D and SIRSI-D will be imputed by the means, if missing at random and a sensitivity analysis is performed to ensure robustness. Other missing items, not in the WOSI TSK-SI-D or SIRSI-D, will be treated as such. If more than 15% of the sample have incomplete questionnaires even after email contact, the sampling is extended.

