3.2 Primary endpoints

The primary outcomes of interest are the SIRSI and the TSK-SI. The SIRSI has been adapted to the shoulder instability cohort from the Anterior Cruciate Ligament Return to Sport Index (ACL-RSI) by (Gerometta et al., 2018). It is composed of twelve items that are rated on a zero to ten. The single total score is calculated by multiplying the sum of each item and dividing it by 120. The worst score then is zero indicating no psychological readiness to RTS and 100 the best, indicating full psychological readiness to RTS. The TSK-SI is composed of 18 questions scored on a 4 point Likert-Scale from "Strongly agree" to "Strongly disagree". The lowest score is 18, indicating no kinesiophobia and 72, indicating

highest level of kinesiophobia. The outcomes will be assessed electronically between three months and two years after surgery or instability event.

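### Filling missing items with an unspecified mean is not justified by missing at random; the effect is small if few items are skipped, but the plan does not cap it

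*Combined protocol and SAP*

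**What the plan says.** Section 5.3 gives the rule for item non-response: "missing items in the WOSI, TSK-SI-D and SIRSI-D will be imputed by the means, if missing at random". It adds that "a sensitivity analysis is performed to ensure robustness", without naming the method. It does not say whether the mean is that of the item across patients, of the patient across the scale, or of a WOSI domain. It gives no maximum number of missing items per patient, no way to judge the missing-at-random condition, and no alternative if that condition is doubted.

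The same section has three controls on missingness. The electronic form prompts, although skipping remains possible: "patients are reminded if a question is not filled in but proceeding is possible". A researcher contacts patients who leave an item blank. Finally, "If more than 15% of the sample have incomplete questionnaires even after email contact, the sampling is extended".

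Section 5.2 names the results that depend on the item data. Internal consistency "will be assessed using Cronbach's alpha coefficient". Also, "Construct validity will be evaluated through factor analysis to confirm the underlying factor structure of the questionnaire". Scores are then compared with the SSV and WOSI.

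**The concern.** Missing at random means that, given what was observed, missingness does not depend on the unobserved values. Methods that use the observed values correctly, such as full likelihood or multiple imputation, are valid under it. A single mean ignores most of that information and then treats the filled value as observed. The condition also cannot be confirmed from the data, so it cannot serve as a switch for the rule.

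In a trial that only needs a total score, this is often a minor matter. Here the inter-item correlations are themselves the result. Item-mean filling inserts a constant unrelated to the patient's other answers, which weakens those correlations and pulls the patient toward the sample average. Person-mean filling inserts a value built from the patient's other answers, which can make items look more alike than they are. The sign of the error therefore depends on a choice the plan leaves open. Section 7.2 acknowledges that some questions may be uncomfortable to answer, so skipping need not be spread evenly over items.

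**Working it through.** **The plan's own figures.** The documents give no figure for the imputation rule. The sample size reproduces: 117 × 1.15 = 134.55, rounded to 135. Nothing below changes it.

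**Inputs from the documents.** SIRSI: 12 items rated 0 to 10 (section 3.2). TSK-SI: 18 items on a 4-point scale (section 3.2). Planning alpha for the SIRSI 0.96 and planning correlation 0.71 (section 4.4). Trigger: 15% of patients incomplete (section 5.3).

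**Assumptions.** TSK-SI alpha 0.80 (section 4.4 says no planning data exist); one factor; normal items; n = 135; 150 simulated datasets per scenario. Missingness is either completely at random (MCAR) or dependent on an observed criterion, with high-mean items skipped more often (MAR).

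**Step 1: what the 15% trigger implies.** If each item is skipped independently with probability p, the share of incomplete patients is 1 − (1 − p)^k.
- p = 2%: 21% (k = 12), 30% (k = 18).
- p = 5%: 46%, 60%.
- p = 10%: 72%, 85%.

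All exceed 15%. Solving 1 − (1 − p)^k = 0.15 gives p of about 1.3% (k = 12) or 0.9% (k = 18). To have 5% or 10% of items missing with 15% of patients incomplete, each of those patients must skip 0.05/0.15 = one third or 0.10/0.15 = two thirds of a scale.

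**Step 2: alpha with 15% of patients incomplete.**

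| Missing per incomplete patient | k | Mechanism | Complete data | Item mean | Person mean | Maximum likelihood |
|---|---|---|---|---|---|---|
| 1 item | 12 | MAR | 0.9589 | 0.9568 | 0.9590 | 0.9589 |
| 1 item | 18 | MAR | 0.7919 | 0.7890 | 0.7948 | 0.7915 |
| 3 items | 12 | MAR | 0.9591 | 0.9534 | 0.9596 | 0.9591 |
| 4 items | 18 | MAR | 0.7952 | 0.7848 | 0.8079 | 0.7939 |
| 6 items | 12 | MAR | 0.9596 | 0.9506 | 0.9616 | 0.9595 |
| 9 items | 18 | MAR | 0.7959 | 0.7771 | 0.8314 | 0.7924 |
| 9 items | 18 | MCAR | 0.7934 | 0.7840 | 0.8101 | 0.7927 |

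With one item missing, the largest change is 0.7919 − 0.7890 = 0.0029. Person-mean filling at k = 12 changes alpha by at most 0.9616 − 0.9596 = 0.0020.

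**Step 3: other quantities when half the scale is missing.**
- Score SD relative to complete data, item mean: 0.921 (k = 12, MAR), 0.927 (k = 18, MAR), 0.946 (k = 18, MCAR), so a loss of 7.9%, 7.3% and 5.4%. Person mean: 1.039, 1.079 and 1.021.
- Mean loading under MAR: k = 12, 0.816 becomes 0.786 (item mean) or 0.824 (person mean); k = 18, 0.424 becomes 0.405 or 0.465.
- Correlation with the criterion under MAR: k = 12, 0.712 becomes 0.676 or 0.722; k = 18, 0.703 becomes 0.665 or 0.710.
- Mean error in the imputed patients' scores under MAR, in score SD: k = 12, +0.33 (item mean), −0.31 (person mean), +0.02 (maximum likelihood); k = 18, +0.33, −0.51, +0.11.

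**Step 4: one patient, for illustration.** Suppose a patient answers 3 on ten SIRSI items and skips two whose sample mean is 6 (an assumed value). Item-mean filling gives (10 × 3 + 2 × 6)/120 × 100 = 35. Person-mean filling gives (10 × 3 + 2 × 3)/120 × 100 = 30. The two readings of the rule differ by 5 points.

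**The case against.** The strongest reply is that the plan's controls keep missingness low, so the rule hardly matters. Much of this stands. Item-missing rates of 2% or more, spread independently, would breach the 15% trigger (step 1). At one missing item per incomplete patient, the shift in alpha is far below sampling error: for alpha 0.80 with 18 items and about 115 patients, the 95% interval runs from about 0.74 to 0.85, and the half-scale results also lie inside it. What does not stand is that the controls guarantee the mild case. The trigger counts patients rather than items, and extending recruitment does not remove the incomplete questionnaires or limit how much of one is filled in.

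A second reply is that person-mean scoring is nearly harmless. For alpha on a scale near 0.96 that is right. But the plan does not choose person-mean scoring, and it has no planning data for the TSK-SI.

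A third is that a sensitivity analysis is already planned. That deserves credit, but an undefined analysis cannot be assessed and does not correct the primary estimate.

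A reader might infer that the rule will seriously distort the validation, or that it will make the SIRSI-D look more consistent than it is. The documents support neither: they do not suggest heavy skipping, they do not specify person-mean filling, and at the planning alpha person-mean filling changes almost nothing.

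**Conclusion.** The point holds as a fault of method with a conditional size. Missing at random does not justify single mean imputation, and leaving the type of mean open leaves the direction of the error open in a study whose results are alpha, loadings and score correlations. The effect is negligible if incomplete patients miss one item each. It becomes noticeable if they skip large parts of a scale, which the plan neither predicts nor limits.

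The direction for item-mean filling held under both missingness mechanisms. The sizes are illustrative: they rest on normal one-factor items, an assumed missingness mechanism and, for the larger alpha shifts, an assumed TSK-SI alpha of 0.80. A change is worth making because it is cheap and can be fixed in the preregistered analysis plan (section 5.4) before data are seen.

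**What to change.** Amend section 5.3, with a cross-reference in section 5.2:

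- Estimate alpha and the factor model from the observed item responses by full-information maximum likelihood, or by item-level multiple imputation. Pairwise correlations are not a good substitute, because they generally need missing completely at random.
- For total scores, use item-level multiple imputation with a modest predictor set: the other items of the scale, WOSI, SSV and sSSV.
- Keep missing at random in the text, but as a stated assumption of the primary analysis rather than a condition to be checked. Removing the phrase would hide an assumption that both recommended methods still need.
- Define the planned sensitivity analysis, for example person-mean scoring with a stated maximum number of missing items per scale, and complete cases. Complete cases can also be biased under missing at random, so they serve as a comparison and not as the reference.
- Report the number of missing items per patient and per item, so readers can see which case in the table above applies.

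The cost is a few sentences, some extra R programming and slightly wider intervals. No change to N=135 or to data collection is needed.

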5.4 Statistical quality considerations

The statistical analysis plan will be preregistered at clinicaltrials.gov (https://clinicaltrials.gov/, accessed at 10.04.2024).

6 REGULATORY ASPECTS AND SAFETY

6.1 Local regulations / Declaration of Helsinki

This research project will be conducted in accordance with the protocol, the Declaration of Helsinki (World-Medical-Association, 2018) ,the principles of Good Clinical Practice, the Human Research Act (HRA) (Eidgenossenschaft, 2011) and the Human Research Ordinance (HRO) (Bundesrat, 2013) as well as other locally relevant regulations. The project leader acknowledges his responsibilities as both the project leader and the Sponsor.

6.2 (Serious) Adverse Events and notification of safety and

protective measures

An Adverse Event (AE) is any untoward medical occurrence in a patient or a clinical investigation subject which does not necessarily have a causal relationship with the trial procedure. An AE can therefore be any unfavourable or unintended finding, symptom, or disease temporally associated with a trial procedure, whether or not related to it.

A Serious Adverse Event (SAE) (ClinO, Art. 63) is any untoward medical occurrence that Results in death or is life-threatening,

Requires in-patient hospitalisation or prolongation of existing hospitalisation, Results in persistent or significant disability or incapacity, or Causes a congenital anomaly or birth defect

Both Investigator and Sponsor-Investigator make a causality assessment of the event to the trial intervention (see table below based on the terms given in ICH E2A guidelines). Any event assessed as possibly, probably or definitely related is classified as related to the trial intervention.

Relationship	Description	
Definitely	Temporal relationship	
	Improvement after dechallenge*	
	Recurrence after rechallenge	
	(or other proof of drug cause)	
Probably	Temporal relationship	
	Improvement after dechallenge	
	No other cause evident	
Possibly	Temporal relationship	
	Other cause possible	
Unlikely	Any assessable reaction that does not fulfil the above conditions	
Not related	Causal relationship can be ruled out	
*Improvement after dechallenge only taken into consideration, if applicable to reaction		

Both Investigator and Sponsor-Investigator make a severity assessment of the event as mild, moderate or severe. Mild means the complication is tolerable, moderate means it interferes with daily activities and severe means it renders daily activities impossible.

6.2.1 Reporting of SAEs (see ClinO, Art. 63)

All SAEs are documented and reported immediately (within a maximum of 24 hours) to the Sponsor-Investigator of the study.

If it cannot be excluded that the SAE occurring in Switzerland is attributable to the intervention under investigation, the Investigator reports it to the Ethics Committee via BASEC within 15 days.

Recurrent instability events (as defined above) are a common occurrence in treatment of shoulder surgery and are not considered as due to the intervention of this study (i.e. usage of a questionnaire).

6.2.2 Follow up of (Serious) Adverse Events

Any (S)AEs that occur and prolong over the termination of the study will be followed up via the treating surgeon according to the routine of the clinic. The research team will be in contact with this respective surgeon and evaluate, if the (S)AE interferes with the interpretability of the data

6.2.3 Notification of safety and protective measures (see ClinO, Art 62, b)

If immediate safety and protective measures have to be taken during the conduct of the study, the investigator notifies the Ethics committee of these measures, and of the circumstances necessitating them, within 7 days.

6.3 (Periodic) safety reporting

An annual safety report (ASR) is submitted once a year to the local Ethics Committee by the Investigator (ClinO, Art. 43 Abs 1).

6.4 Radiation

No radiation expose due to this study is expected.

6.5 Amendments

Substantial changes to the study setup and study organization, the protocol and relevant study documents are submitted to the Ethics Committee for approval before implementation. Under emergency circumstances, deviations from the protocol to protect the rights, safety and well-being of human subjects may proceed without prior approval of the Ethics Committee. Such deviations shall be documented and reported to the Ethics Committee as soon as possible.

Substantial amendments are changes that affect the safety, health, rights and obligations of participants, changes in the protocol that affect study objective(s) or central research topic, changes of study site(s) or of study leader and sponsor (ClinO, Art. 29).

A list of all non-substantial amendments will be submitted once a year to the competent EC together with the ASR.

6.6 Notification and reporting upon completion, discontinuation or interruption of the study

If, during the research project, circumstances arise which could jeopardise the safety or health of the participants or lead to a disproportionate relationship between the risks and burdens and the benefits, all the measures required to ensure protection are to be taken without delay. The project leader is promptly notified (within 24 hours) if immediate safety and protective measures have to be taken during the conduct of the research project. The Ethics Committee will be notified via BASEC of these measures and of the circumstances necessitating them within 7 days.

The Sponsor-Investigator and any other competent authority may terminate the study prematurely according in case of ethical concerns, *i*nsufficient recruitment or when the safety of the participants is doubtful or at risk. Upon premature study termination or study interruption, the Ethics Committee is notified via BASEC within 15 days.

Upon project completion or discontinuation, the Ethics Committee is notified within 90 days. The TMF including the written signed consents are stored in the archives of the Schulthess Klinik Zürich, the project database is stored electronically within the REDCap database. The data will remain coded. The patient identification will be known only at the respective project site by authorized personnel who are bound to confidentiality by contract.

A final report is submitted to the Ethics Committee via BASEC within a year after completion or discontinuation of the study.

6.7 Insurance

Because this is Category A1 with minimal risk, there is no insurance requirement (Art. 12 HRO and insurance is through the clinic's liability).

7 FURTHER ASPECTS

7.1 Overall ethical considerations

The participation of patients is voluntary. Withdrawal is possible without justification at any time without prejudice for further routine treatment and follow-up. This project and related data analyses are conducted in compliance with the protocol, the current version of the Declaration of Helsinki, the ICH-GCP or ISO EN 14155 (as far as applicable) as well as all national legal and regulatory requirements of the HFG and HFV. Patients have the right to know any information derived from participating to this project. In this project, we do not foresee any incidental findings that should not be communicated to the concerned patients. Upon agreement by a patient, medical information can be provided to the family doctor, or other treating physicians to ensure his/her well-being. This project complies with the regulatory requirements of the HRA and HRO. The prerequisite for carrying out the research project is the approval of the Cantonal Ethics Committee.

7.2 Risk-Benefit Assessment

Patients provide time effort of approximately 15 minutes and five minutes to complete two rounds of online questionnaires. Health-related risk is negligible. The Patient questionnaires may be perceived long by participants and address issues that could be embarrassing to respond to (e.g. anxiety, unpreparedness, inadequateness). It is considered that these project-specific procedures provide only minimal risk and discomfort to the patients. There is no clinical risk identified for the participants associated with the data collection described in the protocol.

Confidentiality risk associated with non-anonymized individual data being published is kept to minimum by strict confidentiality rules. No personal individual data will be captured into the project database, except the patients' email address that will be exclusively used to send project questionnaire for electronic data capture. Email addresses will not be exported from the REDCap database and therefore remain protected from unauthorized access.

This study provides a questionnaire to measure psychological readiness to return to sport after shoulder instability and an analysis of its validity and reliability. There is currently no tool available for the German speaking population, hence this part of treatment is left to subjective interpretation or related measures like strength, range of motion or anamnesis.

Once the SIRSI is culturally adapted to the German population meaning Switzerland, Germany and Austria, it will help clinicians and researcher to objectively estimate the ability to RTS. For patients this means a safer RTS and potentially reduces the risk of reinjury.

The subjects will not benefit directly/explicitly from the participation in this study.

7.3 Rationale for the inclusion of vulnerable participants

Not applicable. No vulnerable patients will be enrolled in this study.

